We expect a **sample size of 60** surgical cases, evenly split between the new treatment and control groups, to have a study powered to **detect at least a 1 cm³ difference in orbital volume** between the groups. The sample size calculation was based on using a two-sample Student's t-test to compare the difference in contralateral orbital volume between the treatment and control groups. We used a **power of 90%**, alpha level of .05, and 1.17 cm³ standard deviation of orbital volume. The 'normal' orbital volume and standard deviation were estimated from the results of Forbes et al. (1984). Sample size calculations were performed with the 'power.t.test' function in R statistical software based on Cohen (1988).⁽²⁵⁾ Taking attrition into account, if 25% of our expected patient enrollment numbers are not met for any reason, **our study would still retain a power of 80%**. Additionally, in the event of attrition from loss-to-follow-up alone, our primary outcomes variable and the bulk of the secondary outcomes variables, including the reduction of orbital volume to less than 2 cm³, operative time, traumatic pupillary mydriasis, orbital compartment syndrome, extra-ocular motility, and plate contour, will be successfully obtained on immediate post-operative hour. **Attrition at these stages will have no effect on the above variables.**

Randomization & Statistical Analysis

Cases will be randomized to the treatment or control arms using a pre-generated block randomization scheme with a **block size of 4** and stratified according to surgeon/specialty. In essence, each surgeon will receive their own list of randomized cases to simplify the logistics of the trial. **The block randomization guarantees that at no point during the trial will there be more than a 3-case difference between the treatment and control arms for each individual surgeon**; thus, it is possible but unlikely that there will be a maximum 9 case difference at some

point (sizes will be equal at completion). The randomization scheme has been pre-generated by a statistician, and the resulting trial arm for each case will be placed in envelopes to be revealed at the time of patient enrollment. The treatment will not be blinded to the physician or the patient; it is not practical to keep knowledge of the procedure concealed.

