 - b. Correction of unresolved diplopia (7 to 11 days) in the sitting of soft tissue prolapse with a positive forced duction test.
 - c. Immediate correction of diplopia in the sitting inferior rectus muscle incarceration and a positive forced duction test.
 - d. Immediate correction in a symptomatic patient with orbital floor (trapdoor) fracture that has elicited the oculocardiac reflex.
 - 3- At least 18 years of age.
 - 4- Unilateral orbital floor fracture.
 - 5- No history of orbital trauma.
 - 6- Healthy contralateral orbit.

- 7- Underwent orbital reconstruction.
- 8- Admitted to GMH.
- 9- Returned for the 6-week follow-up.
- Subjects will be excluded from the study enrollment if they:
 - 1- Refuse study enrollment.
 - 2- Are younger than 18 years.
 - 3- Pregnant women.
 - 4- Prisoner
 - 5- Unable to obtain consent (cognitively impaired)
 - 6- Are admitted to hospitals other than Grady Memorial Hospital.

Preoperative Assessment

- All patients, regardless of the group into which they are randomized, will receive a full history and physical examination as part of their admission, including past ocular history.
- A detailed ocular examination will be performed by the same ophthalmology team ([name], ophthalmology attending, or [name], ophthalmology fellow). The ophthalmology team will be blinded to the treatment group.
- This examination will include an evaluation of the following: visual acuity, intraocular pressure, extraocular motility, confrontation visual fields, pupil examination, external examination including Hertel exophthalmometer to document the degree of exophthalmos, slit lamp/penlight exam, dilated fundus exam, and binocular diplopia. These components make up the standard ophthalmologic examination performed for all orbital floor fractures. These data will be abstracted from the medical record before analysis.
- Maxillofacial non-contrast CT scans.
- **The additional workup for group A (treatment group) will include:**

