 - 1) The Digital Imaging and Communications in Medicine (DICOM) image of the pre-op CT scans will be processed using the 3DP computer software to create mirror imaging of the un-injured bony orbit over the fractured orbit. This imaging will be utilized to print a 3D anatomical model. The 3D printing for the enrolled subjects will be performed by [name] and [name]. This will ensure accuracy and limit bias. [name] and [name] are trained to operate the 3D printer software and will follow a standardized approach.

The standardized approach to 3D printing:

- a- A 3D slicer. This is the first software used. Its functions are:
 - Identify the area of interest.
 - Segment the CT DICOM image.
 - Convert the DICOM file into an STL file.
- b- Meshmixer is the second software used. Its functions are:
 - Clean up the printed image.
 - Convert the image to a solid format to facilitate the 3D printing process.
 - Plane cuts and image mirroring.
- c- The third software is the printer's designated software. It facilitates the printing process.

- 2) Once an anatomical model is created, a titanium mesh will be pre-adjusted to the anatomical model. This step will be performed by the designated surgical team and supervised by one of the following attending ([name] for OMFS, [name] for ENT, or [name] for Plastic Surgery). To optimize standardization and reduce bias, the surgical team will standardize the type of orbital plate by using one vendor (Stryker) and will follow the following guidelines to bend the orbital plates:
 - Identify the fracture dimension and location on the printed model.
 - Choose the titanium plate according to the defect dimension.
 - Start bending the plate from the lateral to medial direction. Doing this ensures that defects in the edges overlap and that the fractured bone (defect) is adequately covered.
 - The defect edges are overlapped by 2 mm of the titanium plate.
- 3) The pre-adjusted titanium mesh will be sent to the sterile processing department to be utilized in surgery.

Intra-operative Assessment: Procedures & Treatment

- All operations will utilize general anesthesia.
- A forced duction test of the injured eye will be performed after induction and before extubation in all cases to ensure no entrapment of extra-ocular muscles as the standard of care indicates in these cases.
- All isolated orbital floor fractures will be exposed and identified via a transconjunctival approach.

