- Complex orbital fractures will be exposed and identified via a transconjunctival approach in combination with lateral cantholysis if needed to improve access.
- To record and compare the operative time between the two groups, a stopwatch will be utilized. The time in minutes will be recorded from fracture exposure and identification to final implant placement and fixation.

Postoperative Assessment

During post-operative care, all patients will undergo the following:

- 1) Maxillofacial non-contrast CT scans according to the protocol will be obtained as part of the standard of care in managing orbital fractures.
- 2) The PI will evaluate the orbital volume using OsiriX (medical software). Orbital volume measurements will be obtained to compare the injured and uninjured (contralateral) orbital volumes. OsiriX MD offers advanced processing techniques and has the ability to precisely measure orbital volume. It utilizes the DICOM data from the immediate post-operative CT scans.
- 3) All patients, regardless of the group into which they are randomized, will receive their post-operative assessment by the designated team resident under the supervision of one of the following attendings: [name] for OMFS, [name] for ENT, or [name] for Plastic Surgery.
- 4) All patients, regardless of the group into which they are randomized, will receive their post-operative ocular assessment by [name], ophthalmology attending and Co-PI, or by her fellow [name].

Follow-Up

- All patients will be regularly assessed at 1 week, 3 weeks, and 6 weeks postoperatively.

This is a standard post-operative follow-up schedule for craniomaxillofacial fracture patients. It is also an adequate duration for edema to resolve, which will assist in the accurate evaluation of enophthalmos. The following will be evaluated and recorded by the surgical team at each follow-up visit: enophthalmos, infection, infraorbital nerve injury, traumatic pupillary mydriasis, orbital compartment syndrome, and restricted extra-ocular movement.

- In terms of data collection and data extraction from Epic: PI [name], co-PI [name] and an assigned research coordinator will be involved.

Patient Compensation

All patients enrolled in the study will be compensated with \$100 for their time and to encourage compliance. Their compensation includes the costs of participation in the study (\$50) and the completion of the follow-up visits at week 6.

Data Collection & Analysis

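### Aim 2 eye signs at follow-up are recorded by the unmasked surgical team, although the protocol describes a blinded ophthalmology team whose examination covers the same signs

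*Combined protocol and SAP*

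**What the plan says.** All places are in the combined protocol and SAP.

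- **Follow-Up.** Patients are seen at weeks 1, 3 and 6. "The following will be evaluated and recorded by the surgical team at each follow-up visit: enophthalmos, infection, infraorbital nerve injury"; the list continues with "traumatic pupillary mydriasis, orbital compartment syndrome, and restricted extra-ocular movement".
- **Randomization & Statistical Analysis.** "The treatment will not be blinded to the physician or the patient", on the ground that concealment is impractical.
- **Preoperative Assessment, additional workup for Group A.** On bending the plate to the printed model: "This step will be performed by the designated surgical team and supervised by one of the following attending". The supervising attendings come from OMFS, ENT and Plastic Surgery. Under Postoperative Assessment, item 3, attendings from the same three services supervise the surgical post-operative assessment.
- **Preoperative Assessment.** "The ophthalmology team will be blinded to the treatment group". The examination described there includes "visual acuity, intraocular pressure, extraocular motility, confrontation visual fields, pupil examination, external examination including Hertel exophthalmometer".
- **Postoperative Assessment, item 4.** Every patient, in either group, "will receive their post-operative ocular assessment by [name], ophthalmology attending and Co-PI, or by her fellow". No visit times are given and the blinding is not repeated.
- **Data Collection & Analysis table.** Hertel, motility, pupil and pressure findings are listed by week, without an assessor.

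No section says which team's reading is used when Hypothesis 2 is tested.

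**The concern.** Hypothesis 2 is directional: fewer complications with the pre-adjusted implant. At the follow-up visits the only named recorder is the team that shaped and placed that implant. Enophthalmos is a Hertel side-to-side difference cut at 2 mm, so a small shift in reading moves borderline patients across the line. Restricted motility is also a clinical judgement. Randomisation balances the patients but does not correct readings made with knowledge of the arm, and no later analysis can remove the bias.

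The reason given for an open design applies to the surgeon and the patient. It does not apply to an examiner whom the protocol already describes as blinded. Two teams may also record the same sign with no rule of precedence, which leaves the choice between readings open until the data have been seen.

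**Working it through.** **1. The plan's own figure.** The point does not depend on it, but it supplies the arm size. Inputs from Randomization Sample Size & Calculation: difference 1 cm³, SD 1.17 cm³, alpha 0.05 (taken as two-sided), 60 patients.

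- Standardised difference: 1/1.17 = 0.855.
- 30 per arm: noncentrality 0.855 × √(30/2) = 3.31, power 0.902 (stated 90%).
- 25% shortfall: 60 × 0.75 = 45, or 22.5 per arm; noncentrality 0.855 × √(22.5/2) = 2.87, power 0.800 (stated 80%).

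Both figures reproduce.

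**2. The sections side by side.**

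| | Surgical team | Ophthalmology team |
|---|---|---|
| Knows the arm | Yes: open design, bends the Group A plate | Blinded, stated only under Preoperative Assessment |
| Examines after surgery | Weeks 1, 3 and 6 | Every patient, timing not stated |
| Hertel, motility, pupils, pressure | On its follow-up list | In its examination as described pre-operatively |
| Infection, infraorbital nerve | On its follow-up list | Not in its examination as described |
| Named as recorder at follow-up | Yes | No |

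**3. How large could the bias be?** The documents give no distribution of Hertel differences and no reading error, so everything in this step is assumed. Let the true side-to-side difference be normal with mean μ and SD 1 mm, the same in both arms, so there is no treatment effect. Group A is read a mm too small and Group B b mm too large. The apparent rates above 2 mm are

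- Group A: 1 − Φ(2 − μ + a)
- Group B: 1 − Φ(2 − μ − b)

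The tail areas needed are P(Z>0.5) = 30.9%, P(Z>1) = 15.9%, P(Z>1.5) = 6.7% and P(Z>2) = 2.3%. Rejection probabilities are two-sided at 0.05 with 30 per arm. They come from summing the two binomial distributions over all tables with p < 0.05, for Fisher's exact test and for the uncorrected chi-square test.

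| μ (true rate) | Shift | A v B | False difference | Fisher | Chi-square |
|---|---|---|---|---|---|
| 0.5 mm (6.7%) | A only, 0.5 mm | 2.3% v 6.7% | 4.4 points | 0.7% | 7.4% |
| 1 mm (15.9%) | none | 15.9% v 15.9% | 0 | 1.8% | 5.2% |
| 1 mm (15.9%) | A only, 0.5 mm | 6.7% v 15.9% | 9.2 points | 8% | 21% |
| 1 mm (15.9%) | both arms, opposite, 0.5 mm each | 6.7% v 30.9% | 24.2 points | 57% | 71% |

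For comparison, Aim 2 cites 3.7% for patient-specific implants against 7–27% for the traditional approach. That is a contrast of 7 − 3.7 = 3.3 to 27 − 3.7 = 23.3 points. The one-arm shifts give false differences in the lower part of that range.

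**4. A second model.** Take a true rate of 27% in both arms.

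- No bias: rejection 2.6% (Fisher) or 4.9% (chi-square).
- A quarter of Group A cases missed: 0.27 × 0.75 = 20% v 27%; rejection 5.3% or 9.2%.
- Half of Group A cases missed and 5% of Group B non-cases overcalled: 0.27 × 0.5 = 13.5% v 0.27 + 0.73 × 0.05 = 30.6%; rejection 25% or 36%.

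At a true rate of 7%, missing a quarter of Group A cases changes almost nothing (0.4% or 4.5%). The pattern matches step 3: bias in one arm mainly distorts the estimate, and frequent false significance needs errors in both arms.

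**The case against.** **Masked post-operative data may already exist.** The blinding sentence carries no time limit, and item 4 of Postoperative Assessment sends every patient to ophthalmology. If the sentence covers the whole trial, the gap is narrower. This stands in part. Even so, the surgical team remains the named recorder at follow-up, and no rule gives the ophthalmology reading precedence.

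**A reader might infer that a blinded team is documented as examining patients at weeks 1, 3 and 6.** The documents do not support that. The blinding is written under the pre-operative heading, and item 4 gives no visit times. Nor do they state that the surgical readings are the ones analysed; the data table names no assessor.

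**A reader might also infer that bias alone would produce the hypothesised benefit.** That is not shown. Means, SD and shifts are assumed. The 24-point contrast needs opposite errors totalling 1 mm, a full assumed SD, and its 30.9% lies above the cited 27%.

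**The signs are not equally exposed.** Compartment syndrome rests on a tonometer reading and pupil size on millimetres. Both are less open to the observer than Hertel and motility. This stands.

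**The remedy is partial.** Infection, judged partly on redness and swelling, and nerve testing stay with the unmasked team. Patients know their arm and could reveal it. The ophthalmology attending is a Co-PI, and a co-PI takes part in data extraction; with names removed, overlap cannot be checked. These points stand and shape the fix.

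**Conclusion.** The concern holds as a cheap improvement to secondary (Aim 2) outcomes. As written, the plan has arm-aware surgeons record enophthalmos and restricted eye movement at every follow-up visit. It leaves unused, or at least undefined, an ophthalmology examination that covers the same signs and that the protocol describes as blinded before surgery.

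The bias is a risk whose size is unknown. Under the assumed 0.5 mm shift in one arm, the false difference in enophthalmos runs from about 4 points (true rate 6.7%) to about 9 points (true rate 15.9%). It is larger only if both arms are misread in opposite directions. The likely harm is a distorted estimate more than a false significant result.

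The conclusion about who records, and what that person knows, rests on the text alone. The conclusion about size rests on assumptions. The primary CT volume is not touched by this point.

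**What to change.** In Follow-Up and Postoperative Assessment:

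1. Make the ophthalmology team's examination the Aim 2 value of record for Hertel and motility, and for pupil size and eye pressure where it takes them. Do this at least at week 6, by when the protocol expects oedema to have resolved.
2. State that the ophthalmology blinding extends to the post-operative examinations. The examiner has no access to the operative note or the 3D-model record until the reading is entered, and patients are asked not to disclose their arm.
3. Keep the examining Co-PI out of the extraction of arm data.
4. Use a surgical-team reading only when the ophthalmology reading is missing. Flag its source and add a sensitivity analysis that excludes such readings.
5. Report as a limitation that infection and infraorbital nerve testing remain unmasked.

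Cost: a few sentences of protocol text and the coordination of existing ophthalmology staff. If they do not already attend week 6, this adds up to 60 examinations. Covering all three visits would add up to 60 × 3 = 180. No new type of examination is needed.
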